4.1 Definitions

Subjects officially enter the screening period following provision of informed consent either directly or via a legally authorized representative (LAR). Screening for eligible subjects will be performed within 3 weeks before randomization.

Eligible, consenting subjects will be enrolled to the study. Prior to enrollment of a subject, the following must occur:

- Confirmation that the subject has signed the informed consent form (ICF).
- Confirmation that the subject meets all of the inclusion and none of the exclusion criteria.

The inclusion and exclusion criteria for enrolling subjects in this study are described in the following sections. Enrollment will occur only if the subject meets all study eligibility criteria and has been assessed by the Investigator as being an appropriate candidate for study participation. If there is a question about any of these criteria, the investigator must consult with the appropriate Sponsor representative and resolve any issues before enrolling a participant in the study. If a participant's clinical status changes (including any available laboratory results or receipt of additional medical records) after screening but before treatment such that he or she no longer meets all eligibility criteria, then the subject should be excluded from participation in the study.

An enrolled subject is one who has been deemed eligible and has been assigned to a treatment group.

4.2 Subject inclusion criteria

To be included in this study, each subject must satisfy all the following criteria:

- Histologically **confirmed solid tumor malignancy** (with polymetastatic spread (more than 3 metastases))
- **High-risk bone metastasis(es)** that is (are) asymptomatic or minimally symptomatic [Rosen et al]:
 - Asymptomatic or minimally symptomatic is defined as follows:
 - Numeric Pain Rating Scale (NRS) score ≤ 2 for the specific lesion(s) (see appendix 1)
 - High-risk is defined as follows:
 - Bulky site of disease in bone (diameter ≥ 2 cm)
 - Disease involving the hip (acetabulum, femoral head, femoral neck), shoulder (acromion, glenoid, humeral head), or sacroiliac joints
 - Disease in long bones with cortical involvement of $>1/3$ in proportion to the diameter of the bone (humerus, radius, ulna, clavicle, femur, tibia, fibula, metacarpals, phalanges)
 - Disease in vertebrae of the junctional spine (C1-2, C7- T1, T12-L1, L5-S1) and/or disease with posterior element involvement or epidural extension (Bilsky epidural

compression score 1a-3; see appendix 7) [Bilsky et al]. The posterior elements of the spine consist of the pedicles, laminae, facets (articular processes), transverse processes, and the spinous process.

- Number of Risk Factors (NRF) prognostic score 0-2 (see section 5.1)
- Age \geq 18 years
- Ability to provide informed consent (either by the patient or by a LAR)
- A female participant is eligible to participate if she is not pregnant, and one of the following conditions applies:
Is not a woman of child bearing potential or

A woman of child bearing potential must have a negative serum pregnancy test at screening (see section 7.1.7) and must use a very effective method of birth control

4.3 Subject exclusion criteria

A subject who meets any of the following criteria must be excluded from the study:

- Previous RT to the target treatment site(s)
- NRF prognostic score 3
- Serious medical co-morbidities that preclude RT
- Bone lesion complicated with a pathological fracture or impending pathologic fracture for which prophylactic stabilization is recommended, characterized by Mirels score of \geq 9 [Mirels et al] (see appendix 8).
- Spinal metastasis with SINS score $>$ 13 (see appendix 6) requiring upfront neurosurgical stabilization [Fourney et al].
- More than 5 high-risk asymptomatic or minimally symptomatic metastatic bone locations

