5.1 Description

Patients will be randomized (1:1) to receive either systemic therapy/observation (Arm A) or early RT plus systemic therapy / observation (Arm B).

Arm A:

The observational arm (Arm A) will include **observation or systemic therapy**, according to the treating physician's discretion. Systemic therapy may include continuation of the current systemic therapy or initiation of a new systemic therapy.

These patients will be able to receive palliative RT to progressed, painful lesions (an SSE) only at the time of symptom worsening (NRS > 2/10 or need for opioids) or determination of spinal cord compression with neurological symptoms or (high risk for) fracture requiring surgical intervention. Upfront preventive RT is not allowed.

Arm B:

The intervention in this study is **early, upfront radiation therapy** to asymptomatic or minimally symptomatic (defined as high-risk) bone metastases. Up to 5 high-risk asymptomatic or minimally symptomatic metastatic locations per patient are allowed.

The radiotherapy (RT) doses used will be in accordance with common practice palliative RT schedules. As such a single fraction of 8 Gy is considered for all patients, except for patients with a very good prognosis (NRF prognostic score 0-1) in which a higher dose will be used with SABR [Chow et al].

Table 3: Predictive model for estimation of median overall survival (OS): NRF-model [Chow et al].

Three variables:

- **Primary cancer type** -> risk factor: non breast/prostate/lung cancer
- **Site of metastases** -> risk factor: metastases other than bone
- **Karnofsky performance score (KPS)** -> risk factor: KPS ≤60

0-1 risk factors	median OS 64 weeks	95%CI: 37-undefined
2 risk factors	median OS 28 weeks	95% CI 22-34
3 risk factors	median OS 10 weeks	95% CI 8-13

Simulation:

All patients will be immobilized in a comfortable and stable position to irradiate the metastatic lesion(s). Support and/or immobilization devices will be used to increase patient comfort or to ensure set-up reproducibility. A planning CT scan will be acquired without intravenous contrast with <3mm CT slice thickness (1mm for SABR) encompassing the region of interest with sufficient margin for treatment planning, a typical scan length should extend at least 10 cm superior and inferior beyond the treatment field borders. The isocenter will be placed in the middle of the affected bone lesion.

Target volume definition:

1. *Conventional radiotherapy:*

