7.2 Efficacy Evaluations

- Comparison of the number of SSE's in both study arms. SSEs are defined as:
 - symptomatic pathological fracture
 - spinal cord compression leading to neurological deficit or pain
 - Indication for palliative radiotherapy (for bone pain, cord compression or (impending) fracture)
 - Indication for orthopedic surgery (for bone pain, cord compression or (impending) fracture)

All SSE's will be recorded in both study arms. Patients in the upfront RT arm may develop an SSE in a bone metastasis that was not previously included in the study, which also needs to be registered. An exception are SSE's in bone metastases that were already treated with surgery or RT before study participation

Patients in the upfront RT arm developing new minimally symptomatic or asymptomatic high-risk bone metastases during study participation are strongly advised to further be treated with preventive RT. Details concerning the characteristics of these new high-risk metastases as well as details regarding the preventive RT must be captured in the eCRF.

- Comparison of the number of **hospitalizations** related to the high-risk bone metastasis(es) between observation/systemic therapy and upfront RT plus observation/systemic therapy
- **Overall survival:** from time of study randomization to date of death of any cause or last follow-up visit (24m after randomization date)
- To compare **quality of life** between observational arm (arm A) and upfront RT arm (arm B), using the EORTC QLQ-C15-PAL form and the EuroQol Group EQ-5D-5L form

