9.1 Justification of sample size

In collaboration with statistical experts UGent a sample size calculation was performed. A hazard ratio of 0.5 is deemed clinically relevant, increasing the estimated 2-year SSE free survival from 20% to 45%. Assuming exponentially distributed SSE-free survival, setting alpha to 0.05 and the required power to 0.8 and assumed non-informative drop out to 20%, this results in a sample size of 120 (96 without drop out) with a required number of events of 65.

Hazard ratio (HR) = 0.5 is in between previously observed effect sizes in similar settings: Different trials analyzing the use of bone modifying agents with the presence of SREs, showing a HR around 0.7 [Smith et al; O’Carrigan et al; Rosen et al]]. In the above-mentioned phase II trial [Rosen et al] there was a large reduction in SREs from incidence from 29% to 1.6% at 1 year in the RT group. Because in our trial SSEs and not SREs will be analyzed, we expect a more conservative HR. This was also demonstrated in a trial comparing skeletal-related events with symptomatic skeletal events for two different bone modifying agents [Smith et al].

A sample size of 96 patients was calculated to have an 80% power and an $\alpha < 0.05$. With an estimated dropout of 20%, the **total sample size will be 120** with a required number of events of 65.

Each patient will be stratified by their prognostic class (0-1 vs 2), high-risk disease location (spine location vs. other) and bone modifying agents (yes vs. no) in this hierarchical order. With 3 stratification factors for randomization, there are 8 strata, which is rather high for only 60 patients per arm. Strata where only 1 arm is present and the events in these strata, are implicitly ignored in the estimation/testing. Strata with less than 10 patients will be merged with the corresponding stratum with the same value for factor A and B, but different value for C in the upfront decided hierarchical order (cfr above).

Randomization will be completed on a per patient basis (not lesion based), even though each patient may have up to 5 multiple sites of metastatic bony disease.

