9.3 Statistical methods for analysing primary and secondary outcomes

Primary objective:

The primary endpoint (SSE-free survival) is a composite endpoint of SSEs and death (death before SSE is part of the endpoint, not a competing risk). The primary endpoint is time until the occurrence of SSE in any bone metastasis or death from the date of randomization whichever occurs first. Data suggest that the median SSE-free survival is around 10.4 months. With a HR of 0.5, we hypothesize that the median SSE-free survival will be 20.8 months.

A proportion of patients will have multiple high-risk bone lesions. Pain will be reported lesion-based, however the SSE-free survival remains patient-based as this is more clinically relevant.

Secondary objectives

- The number of **hospitalizations** related to the high-risk metastase(s) will be compared between systemic therapy / observation (arm A) and upfront RT plus systemic therapy / observation (arm B) from date of study randomization to last follow-up visit (24m after randomization date), date of death of any cause or early end of participation in the study due to other reasons
- **Overall survival** will be assessed from time of study randomization to date of death of any cause or last follow-up visit (24m after randomization date)
- **Quality of life** will be compared between systemic therapy / observation (arm A) and upfront RT plus systemic therapy / observation (arm B), using the EORTC QLQ-C15-PAL questionnaire (see appendix 2) and the EuroQol Group EQ-5D-5L questionnaire (see appendix 3)
- **Adverse events** in both study arms will be evaluated using the National Cancer Institute Common Terminology Criteria for Adverse Events (NCI-CTCAE) v5.0 (see appendix 4) from the time of ICF signing to last follow-up visit (24m after randomization date), date of death of any cause or early end of participation in the study due to other reasons. Only adverse events that are related to the bone metastatic disease or related to the radiotherapy (only for patients in arm B) will be reported in the eCRF.

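### The protocol gives two answers on whether an SSE in a previously operated target lesion is a primary event: such a lesion may be enrolled, its SSE is excepted from registration, yet the endpoint counts any bone metastasis

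*Protocol*

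**What the plan says.** Three sets of rules bear on the same lesion.

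- **Eligibility (protocol 4.3, repeated in the synopsis).** The only exclusion based on earlier local treatment of the target is "Previous RT to the target treatment site(s"). Earlier surgery to the target is not listed, and section 4.2 does not add it. A separate criterion excludes "Bone lesion complicated with a pathological fracture or impending pathologic fracture for which prophylactic stabilization is recommended", with a Mirels score of 9 or more. Another excludes spinal metastases with SINS above 13 that need upfront stabilisation.
- **Registration of SSEs (protocol 7.2, repeated in Table 1 footnote j).** All SSEs are recorded in both arms, including those in lesions not previously part of the study. Then: "An exception are SSE's in bone metastases that were already treated with surgery or RT before study participation".
- **Endpoint (protocol 9.3; the synopsis and Table 2 agree).** "The primary endpoint is time until the occurrence of SSE in any bone metastasis or death from the date of randomization whichever occurs first". None of these three places carries the exception. Section 9.3 adds that "the SSE-free survival remains patient-based as this is more clinically relevant", and section 5.1 says "Up to 5 high-risk asymptomatic or minimally symptomatic metastatic locations per patient are allowed".

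**The concern.** For previous RT, eligibility and the exception fit together. An irradiated site cannot be a target, so the exception reaches only lesions outside the study. For previous surgery they do not fit. A target lesion that was operated on and never irradiated falls under the exception, although it is one of the lesions the trial is randomising patients to have irradiated or observed.

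A site that sees a fracture in such a lesion would leave it unregistered under 7.2 but should count it under 9.3. An event that is not registered cannot reach the analysis, so in practice the registration rule may override the endpoint definition. At stake are some events in the lesions the hypothesis is about, some dilution of the treatment comparison, and a count that could differ between sites according to which section they follow.

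**Working it through.** **1. The rules side by side**

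| Rule | Earlier RT to the lesion | Earlier surgery, no RT |
|---|---|---|
| 4.3: may it be a target? | No | Yes, if no other criterion bars it |
| 7.2 and footnote j: is an SSE in it registered? | No (non-study lesion only) | No, read literally |
| Synopsis, Table 2, 9.3: is it a primary event? | Yes, any bone metastasis | Yes, any bone metastasis |

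The last two rows disagree in both columns. Only in the surgery column does the disagreement reach an enrolled lesion.

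**2. Do other criteria close the gap?** Only partly. The fracture criterion removes some operated lesions. The Mirels and SINS criteria describe stabilisation still needed, not stabilisation already done. A long bone fixed before any fracture, or an operated vertebra, could still be high-risk with NRS of 2 or less.

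**3. The plan's own figures.** Inputs from 9.1: HR 0.5, alpha 0.05 (taken as two-sided, which reproduces the plan), power 0.80, 20% two-year SSE-free survival in the control arm, 20% drop-out.

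- Events = 4(1.960 + 0.842)² / (ln 0.5)² = 65.35; the plan states 65.
- Arm B two-year survival = 0.20^0.5 = 0.447. Mean event probability over 24 months = (0.800 + 0.553)/2 = 0.676.
- Patients = 65/0.676 = 96.1; the plan states 96. With drop-out, 96/0.8 = 120, as stated.
- Power with 65 events = Φ(√(65/4) × 0.693 − 1.960) = 79.8%.

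The design reproduces and has no spare events.

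**4. Possible size.** The share f of affected patients is not in the protocol. I take 1 to 5% purely as an assumption.

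*Full dilution:* HR is 1 in affected patients and the log hazard ratio shrinks in proportion, so power = Φ(√(65/4) × (1 − f) × 0.693 − 1.960).

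- f = 1%: 79.0%
- f = 2%: 78.2%
- f = 5%: diluted HR = exp(−0.95 × 0.693) = 0.518; power 75.6%

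*Lost events only:* HR stays at 0.5, and affected patients lose a share s of their event hazard in both arms. The base is 96 × 0.676 = 64.9 events.

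- f = 2%: 64.5 events (s = 0.5) to 63.6 (s = 1); power 79.5% to 79.0%
- f = 5%: 63.8 events (s = 0.5) to 61.7 (s = 1); power 79.1% to 77.7%

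The case s = 1 is an upper bound, because deaths and SSEs in other lesions still count.

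**The case against.** A reader might infer that SSEs in operated target lesions can never count, that some randomised lesions therefore certainly cannot produce a primary event, and that power drops markedly. The documents do not support that much.

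- **The exception can be read narrowly.** In 7.2 and footnote j it follows directly on the mention of lesions not previously included in the study, so it may be meant for those alone. This reading is open but not secure: the statement of purpose for Amendment 2 attaches the exception to SSEs in any bone metastasis.
- **If 9.3 governs, nothing is lost.** The events then count, and what remains is an inconsistency. This stands, and it is why the point is a contradiction and not a demonstrated loss of events.
- **The affected group is probably small.** The fracture, Mirels and SINS exclusions shrink it, up to five locations may be enrolled per patient, and nothing shows that any operated target will be enrolled. This stands.
- **HR of 1 in affected patients is pessimistic.** The endpoint is patient-based. Arm B patients are strongly advised to have preventive RT to new high-risk lesions. The background section also hopes for a survival effect. This stands, so full dilution is an outer bound.
- **Bias between arms.** One might infer that unblinded sites could decide after an SSE whether the exception applies. But earlier surgery is a dated fact in the record, open to source data verification, and the rule is the same in both arms. Sections 7.1.1 and 7.1.5 do not name earlier bone surgery among the screening items. The list in 7.1.1 is not exhaustive, however, and the eCRF is not shown. At most a small risk of classification after the event remains.

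None of this removes the disagreement between the registration rule and the endpoint definition.

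**Conclusion.** Wrong as written: the protocol contradicts itself on the primary endpoint. Sections 4.3, 7.2, footnote j, the synopsis, Table 2 and 9.3 must be reconciled. The contradiction holds however common operated targets are.

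Its numerical effect is probably small. With an assumed 1 to 5% of patients affected, power goes from 79.8% to about 79 to 76% under full dilution, and to no lower than about 78% if only events are lost. These figures rest on an assumed frequency and on the two simple mechanisms shown, not on anything the protocol reports. The loss is per lesion, not per patient: someone with an operated target can still reach the endpoint through death or an SSE elsewhere. The expected consequence is some lost events or mild dilution in both arms, not a systematic bias between them.

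**What to change.** 1. In 7.2 and Table 1 footnote j, state that the exception applies only to metastases not enrolled as study lesions, so that an SSE in any enrolled lesion always counts.
2. Carry the same exception into the endpoint definition in the synopsis, Table 2 and 9.3, so that registration and analysis follow one rule.
3. Before randomisation, record in the eCRF which bone sites were previously operated on or irradiated, so that the exception is settled before allocation is known.

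The cost is one sentence in each place and one eCRF field. No patients or visits are added, and eligibility is unchanged.

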4.4 Study restrictions

Subjects will be informed and reminded of all study restrictions during recruitment, the informed consent process, and during screening and other scheduled assessments. Compliance with all restrictions will be required for the duration of the study.

4.4.1 Contraceptive requirements

Pregnant women are excluded; as well as women of child-bearing potential who are unwilling or unable to use a very effective method of birth control. Child-bearing potential is defined as follows: A woman is considered of child-bearing potential, i.e. fertile, following menarche and until becoming postmenopausal, unless permanently sterile. Permanent sterilization methods include hysterectomy, bilateral salpingectomy and bilateral oophorectomy. Tubal ligation is NOT a method of permanent sterilization. A postmenopausal state is defined as no menses for 12 months without an alternative medical cause. Very effective methods of birth control are sterilisation and, in case of optimal use, condoms and hormonal contraception. However, no contraceptive is 100% reliable.

4.4.2 Other lifestyle considerations and study restrictions

No lifestyle restrictions apply.

HERMES/CTO23032GZA – Protocol v3.0 07-OCT-2024

32/70

Clinical Trials Oncology

Ref.Nr.: P.01-S.23

Versie: 6.0

4.4.3 Prior and concomitant therapies

Patients treated with prior or concomitant systemic therapy are eligible for this study. The decision for (dis)continuation is left at the discretion of the treating physician.

All pain medication (including corticoids), bone-modifying agents and anticancer therapy used within 7 days prior to the screening visit and through the end of the study will be recorded. The dates of administration, method of administration, dosage, and reason for use will be included. There are no restricted or prohibited medications.

4.5 Screen failures

A screen failure is a consented subject who has been deemed ineligible on the basis of one or more eligibility criteria or who has withdrawn consent prior to treatment assignment.

Patients who sign an informed consent but fail to start with treatment for any reason will be considered a screen failure. The reason for not starting with treatment will be recorded on the subject screening and enrollment log. Collection of information on screen failure is required to ensure transparent reporting of screen failure participants, to meet the Consolidated Standards of Reporting Trials Publishing Requirements and to respond to queries from regulatory authorities. The required information includes date of consent, demography, screen failure details, eligibility criteria, and any (serious) adverse events.

Rescreening (*e.g.* for a metastasis in a different location) can be permitted in this study, after agreement between the investigator and the sponsor. The minimal number of procedures from the initial screening that should be repeated must be discussed with the study responsible physician.

The investigator agrees to complete a participant identification and enrollment log to permit easy identification of each participant during and after the study. This document will be reviewed by the Sponsor study-site contact for completeness. The participant identification and enrollment log will be treated as confidential and will be filed by the investigator in the study file. To ensure participant confidentiality, no copy will be made. All reports and communications relating to the study will identify all participants by participant identification number (see Section 5.2).

5. Study intervention

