3.1 General scheme of study design

The HERMES study is a phase III randomized controlled trial to investigate if early, upfront RT for asymptomatic or minimally symptomatic high-risk bone metastases can prevent symptomatic skeletal events. The primary outcome is the time to a symptomatic skeletal event (SSE) or death due to any cause. Secondary outcomes are overall survival, early and late adverse effects, quality of life and need for hospitalization related to the high-risk bone metastase(s).

The study will be conducted in various centers (inter)nationally.

Participation in the HERMES study will comprise a screening period, during which the screening assessments must be completed. Eligible, consenting subjects will then be randomized (1:1) into one of two treatment arms: an observational arm (arm A) receiving systemic therapy / observation or an upfront RT arm (arm B) receiving upfront RT plus systemic therapy / observation. RT should take place within 21 days after date of randomization for subjects in arm B. Afterwards, onsite follow-up visits will take place at 1, 3, 6, 12, 18 and 24 months after date of randomization during which safety and efficacy are monitored.

The screening, treatment and follow-up schedules are presented in Table 1. A schematic presentation of the study design is shown in Figure 1.

Abbreviations: R = Randomization

Figure 1: Schematic representation of study design of the HERMES study.

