6.1.2 Treatment planning and treatment period

Upon enrollment in the study, patients will be randomized into either the observational arm receiving observation / systemic therapy (arm A) or the upfront RT arm receiving upfront RT plus systemic therapy / observation (arm B).

For patients randomized in arm B, radiotherapy will start within 21 days after the date of randomization. Treatment planning and delivery is described in section 5.1.

Any toxicity (graded according to CTCAE v5.0) that occurs during this period should be entered in the database. AE that took place during this treatment period will be documented at the first follow-up visit.

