9.2 Population description

Patients suffering from asymptomatic or minimally symptomatic high-risk bone metastases will be screened for inclusion in this HERMES study. Data will be analyzed in accordance with the subjects' randomized treatment assignment.

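### Sections 4.1 and 4.5, as worded, permit removal of randomised patients who have not started treatment; this contradicts section 9.2 and the follow-up rules, and literal use would tend to favour RT

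*Protocol*

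**What the plan says.** Two rules set the cut-off at treatment.

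- Section 4.5: "Patients who sign an informed consent but fail to start with treatment for any reason will be considered a screen failure". The data it requires for a screen failure are consent date, demography, failure details, eligibility and adverse events. SSE and survival follow-up are not listed.
- Section 4.1: a patient whose clinical status changes "after screening but before treatment such that he or she no longer meets all eligibility criteria, then the subject should be excluded from participation".

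The timing is fixed elsewhere. Section 3.1: "Eligible, consenting subjects will then be randomized (1:1) into one of two treatment arms". Section 5.2 places randomisation between screening and the start of treatment. Section 6.1.2 says that in arm B "radiotherapy will start within 21 days after the date of randomization". Section 9.3 counts the primary endpoint (SSE or death) from the randomisation date.

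Other text points the opposite way.

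- The first sentence of 4.5 ties screen failure to ineligibility, or to consent withdrawn before an arm is assigned.
- The last sentence of 4.1 treats a patient as enrolled once an arm is assigned.
- Table 1 footnote h, attached to the treatment and follow-up periods, requires immediate reporting of an SSE and then survival and further SSE data to 24 months.
- Footnote k and section 6.3.1 continue survival and SSE collection after discontinuation without withdrawal of consent.
- Section 7.2 records all SSEs in both arms, except in bone metastases treated before the study.
- Section 9.2: "Data will be analyzed in accordance with the subjects" randomised arm.

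**The concern.** A cut-off at treatment rather than at randomisation allows exclusions during time in which primary events already count. The reasons for exclusion overlap with the endpoint. A patient who dies while waiting for RT has failed to start treatment. A new pathological fracture breaches an exclusion criterion and, if symptomatic, is an SSE. Losses of this kind are informative, whereas the sample size assumes that they are not: "setting alpha to 0.05 and the required power to 0.8 and assumed non-informative drop out to 20" per cent.

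The rules are unlikely to bite equally in the two arms. Arm B has a defined study treatment with a wait of up to three weeks. For an arm A patient under observation, or continuing current systemic therapy, there is no start to fail. Removing early events mainly from arm B lowers its apparent hazard.

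The defect also goes beyond the definition of an analysis set. If sites treat a randomised patient as a screen failure and stop follow-up, no later analysis plan can recover the missing outcomes.

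**Working it through.** **1. The plan's own figure.** Section 9.1: "A hazard ratio of 0.5 is deemed clinically relevant, increasing the estimated 2-year SSE free survival from 20% to 45" per cent, and "this results in a sample size of 120 (96 without drop out) with a required number of events of 65". By Schoenfeld's formula with 1:1 allocation and two-sided alpha 0.05 (sidedness is not stated, but two-sided reproduces the figure), events = 4 × (1.960 + 0.842)² / (ln 0.5)² = 65.3. The mean 24-month event probability is (0.80 + 0.55)/2 = 0.675; 65/0.675 = 96.3; 96/(1 − 0.20) = 120. The stated figures are reproduced.

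**2. Events in the waiting window.** The control hazard is −ln(0.20)/24 = 0.0671 per month (median 10.3 months; section 9.3 gives 10.4). Twenty-one days are 21/30.44 = 0.690 months.

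- P(event within 21 days) = 1 − exp(−0.0671 × 0.690) = 4.5%. Of 60 arm B patients that is 2.7. Of 48 (section 3.2.2 speaks of 48 per arm) it is 2.2.
- If RT starts are spread evenly over 0 to 21 days, the probability is about 2.3%, or 1.4 of 60.

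As a plausibility check, the median survival figures in Table 3 of section 5.1 imply deaths within three weeks of 1 − 0.5^(3/64) = 3.2% (NRF 0-1) and 1 − 0.5^(3/28) = 7.2% (NRF 2). A 4.5% risk of SSE or death is therefore not an exaggerated input.

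**3. Effect on the comparison.** Simulation: 60 per arm; control hazard as above; arm B at the control hazard until RT and then multiplied by the hazard ratio; 24 months of follow-up; exponential drop-out of 20% over 24 months; unstratified log-rank test; 20,000 runs per row. All randomised patients are compared with the worst case, in which every arm B patient with an event before RT is deleted and arm A is left untouched.

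| True HR after RT | RT start | Dropped | HR: all → deleted | Significant in favour of RT: all → deleted |
|---|---|---|---|---|
| 1.0 | even over 0-21 days | 1.4 | 1.00 → 0.97 | 2.6% → 3.4% |
| 1.0 | all on day 21 | 2.7 | 1.00 → 0.94 | 2.5% → 4.6% |
| 0.5 | even over 0-21 days | 1.4 | 0.51 → 0.49 | 82% → 87% |
| 0.5 | all on day 21 | 2.7 | 0.52 → 0.47 | 79% → 88% |

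A repeat with 40,000 runs per row gave 3.6% and 4.8% for the two null rows after deletion, and the same hazard ratios to within 0.01. The null rates are thus known to about 0.2 percentage points.

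**4. Non-starters with a poor prognosis (assumption).** The protocol gives neither the share of non-starters nor their risk. Suppose that a further 5% to 10% of arm B never start and are deleted. At the same hazard as other patients, the null HR is 0.94 and the false-positive rate 4.5% to 4.9%, close to the day-21 row. At 2 to 3 times the hazard, the HR is 0.86 to 0.92 and the rate 6% to 10%.

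**The case against.** The strongest reply is that the plan already says the right thing. Section 9.2 analyses by randomised arm, footnote h covers the very window in dispute, 6.3.1 continues follow-up after discontinuation, and nowhere is it said that screen failures leave the primary analysis. The loss-of-eligibility sentence in 4.1 sits in a paragraph about eligibility before enrolment, and the analysis set may be defined in an analysis plan that is not shown.

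Much of this stands. It rules out saying that such patients are dropped as a settled matter. It does not remove the conflict: 9.2 says how patients are grouped, not that every randomised patient is included, and 4.5 tells sites to class a non-starter as a screen failure, for whom no outcome follow-up is listed.

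A reader might infer several stronger things that the protocol does not support.

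- *That the exclusion operates in arm B only.* Neither rule names an arm or equates treatment with RT, and arm A may begin a new systemic therapy that also fails to start.
- *That every deterioration while waiting is an event lost from arm B and kept in arm A.* A fall to NRF 3 is not a primary event in either arm. Pain above NRS 2 alone is not an SSE under section 2; an indication for palliative RT or surgery, a symptomatic fracture or cord compression is needed. An arm B patient who becomes painful and still receives RT has started treatment, so the 4.5 rule would not apply. Deleting every event before RT is therefore an upper bound for that mechanism.
- *That a patient could be randomised twice.* Rescreening needs sponsor agreement, and the example given is a metastasis elsewhere. The text does not bar rescreening after randomisation, but nothing provides for a second allocation.

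**Conclusion.** The point holds as a contradiction in the protocol with a directional risk, not as a demonstrated one-arm exclusion. Read literally, 4.1 and 4.5 allow randomised patients to be removed for reasons related to the outcome; at least six other places in the protocol point the other way.

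If the literal reading were applied to all arm B events before RT, the bias would favour RT but be modest: a null hazard ratio of 0.94 to 0.97, a one-sided false-positive rate of about 3.5% to 4.6% instead of 2.5%, and, with a true hazard ratio of 0.5 after RT start, an estimate of 0.47 to 0.49 instead of 0.51 to 0.52. These figures assume a constant hazard from randomisation, 60 per arm and deletion in arm B alone. Rates of 6% to 10% need assumptions about non-starters that the protocol does not give, so they show sensitivity and are not a forecast. The matter is worth correcting prospectively because follow-up that was never collected cannot be restored at analysis.

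**What to change.** - Section 4.5: limit screen failure to consented patients who are not randomised, and state that rescreening applies only before randomisation.
- Section 4.1: for exclusion from participation after loss of eligibility, replace *before treatment* with *before randomization*. This governs study status, follow-up and analysis only. It takes no position on whether RT is given to a patient whose condition changes, which stays with the treating physician.
- Sections 4.5 and 9.2: state that every randomised patient, whether or not treatment starts, is followed for SSE and survival to 24 months, subject to consent, and analysed in the assigned arm from the randomisation date.

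The cost is a few sentences in a protocol amendment and a matching instruction to sites. The 65 events, the sample size of 120 and the visit schedule are unchanged.
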